## 2) Type of Participant and Target Disease Characteristics

- a) Participants must be at least 18 years old and have histological or cytological confirmation of metastatic and/or unresectable metastatic colorectal, pancreatic, breast, ovarian, or urothelial carcinoma with measurable disease per RECIST v1.1 or per PCWG3 criteria for prostate carcinoma (see [Appendix 7](#) or [Appendix 8](#), respectively).
- b) Presence of at least 2 lesions: at least one with measurable disease as defined by RECIST v1.1 (per PCWG3 criteria for prostate carcinoma) for solid tumors for response assessment; at least 1 lesion must be accessible for biopsy in addition to the target lesion.
- c) Participants with lesions in a previously irradiated field as the sole site of measurable disease will be permitted to enroll provided the lesion(s) have demonstrated clear progression and can be measured.
- d) Participants must have received, and then progressed or been intolerant to, at least 1 standard treatment regimen in the advanced or metastatic setting, if such a therapy exists, and have been considered for all other potentially efficacious therapies prior to enrollment. Participants who are ineligible for standard therapy (due to medical factors such as comorbid illness, age, etc.) will be allowed to enroll provided the reason for their ineligibility is documented in their medical records. Specific details are provided in [Section 3](#)) below for each indication.
- e) The Dose Escalation (Parts 1 and 2)
  - i) Participants with colorectal, prostate, urothelial, ovarian, triple-negative breast, or pancreatic carcinoma will be permitted.
  - ii) All comers CD8 TIL are permitted in Parts 1 and 2. However, at least 3 participants with low or mid CD8 TIL must be evaluated at each dose level in Part 2.
- f) The Expansion (Part 3)
  - i) Participants must have tumors classified by CD8+ TILs prior to treatment to determine cohort assignment:
    - (1) Low:  $CD8 < 2\%$
    - (2) Mid:  $2\% \leq CD8 < 20\%$
    - (3) High:  $\geq 20\%$
- g) ECOG performance status  $\leq 2$ .
- h) Prior palliative radiotherapy must have been completed at least 2 weeks prior to the first dose of the study treatment. Participants with symptomatic tumor lesions at baseline that may require palliative radiotherapy within 4 weeks of the first dose of study treatment are strongly encouraged to receive palliative radiotherapy prior to enrollment.

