Participants will receive a maximum of 2 cycles of BMS-986277 monotherapy. Following 2 cycles of BMS-986277 monotherapy, participants may receive optional nivolumab treatment (480 mg Q4W) for up to 26 cycles if eligibility criteria continue to be met (see [Sections 6.1](#) and [6.2](#)) as indicated in [Table 2-5](#). Participants whose disease progresses prior to receiving Cycle 2 of BMS-986277 may also receive nivolumab treatment if eligibility criteria continue to be met, skipping any remaining monotherapy visits and proceeding directly to Cycle 3, optional nivolumab treatment. For participants whose disease has progressed, a minimum of 14 days will be required between the Day 1 BMS-986277 administration (Cycle 1 or Cycle 2) and the start of nivolumab administration. For participants whose disease is responding (complete or partial) per RECIST v1.1 or PCWG3 at the 8 week scan, treatment must be discussed and agreed upon with the Medical Monitor (or designee) prior to the start of the optional subsequent nivolumab treatment.

BMS-986277 and nivolumab (if participant meets subsequent treatment criteria above) will be administered by IV infusion using a syringe pump (nivolumab may also be administered using an infusion bag).

Infusion duration of BMS-986277 will be based on the dose level chosen for Part 1, and will match the infusion duration for that dose level in Part 1. BMS-986277 will be administered over 5 minutes except for the  $3 \times 10^{12}$  vp dose, which will be administered over 15 minutes.

Nivolumab is infused over 30 minutes. Study treatment preparation and administration are described in [Sections 7.1.1](#) and [7.1.2](#).

Participants should receive nivolumab at a dose of 480 mg as an approximate 30 minute infusion on Day 1 of each treatment cycle starting with Cycle 3 until progression, unacceptable toxicity, withdrawal of consent, completion of up to 26 cycles of treatment, or the study ends, whichever occurs first.

At the end of the infusion the administration line should be flushed with normal saline to ensure that the full viral dose has been administered. This flush should only use a sufficient amount of saline to flush the line and should not exceed 30 mL.

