### **9.1.3 Secondary Efficacy Assessments**

The secondary efficacy assessments will include the ORR (eg, PR + CR), DCR, mDOR, mPFS and PFSR at 8, 16, and 24 weeks (dependent on indication) based on assessment of tumor response using RECIST v1.1 or PCWG3.

ORR is defined as the proportion of all treated participants whose best overall response (BOR) is either a CR or PR. BOR is defined as the best response designation over the study as a whole, recorded between the dates of first dose until the last tumor assessment prior to subsequent therapy. For participants whose treatment continued beyond RECIST v1.1 or PCWG3 defined disease progression, BOR is defined as the best response recorded between the dates of first dose until the time of the initial disease progression defined by RECIST v1.1 or PCWG3. CR or PR determinations included in the BOR assessment must be confirmed by a second scan performed no less than 4 weeks after the criteria for response are first met. For those participants who have

surgical resection, only pre-surgical tumor assessments will be considered in the determination of BOR.

DCR is defined as the proportion of all treated participants who have achieved CR, PR, and SD. BOR for a participant will be assessed per RECIST v1.1 or PCWG3 by BICR and/or by investigator, where available.

mDOR, computed for all treated participants with a BOR of CR or PR, is defined as the time between the date of first response and the date of disease progression or death, whichever occurs first.

PFS for a participant is defined as the time from the first dosing date to the date of first objectively documented disease progression or death due to any cause, whichever occurs first. mPFS and PFSR will be assessed at 8, 16, and 24 weeks (indication dependent).

The proportion will be calculated by the Kaplan-Meier estimate, which takes into account censored data.

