### 10.1.2.3 Cohort 3 (≥ 20%)

Cohort 3 is a monotherapy expansion of BMS-986277 which will treat participants with high CD8 TILs (≥20%) to further characterize the pharmacodynamics of BMS- 986277 alone at RD from Part 1. Up to 12 participants evaluable for pharmacodynamic endpoints will be treated in this cohort. Approximately 20% additional participants may be enrolled in this cohort to ensure the number of evaluable participants is achieved. To assess the PD effects, assuming that a biomarker

is measured as a continuous variable, 12 evaluable participants will provide the confidence that the estimate of the ratio of on-treatment biomarker values to baseline values will be within 20% of the true value as shown in Table 10.1.2.3-1.

**Table 10.1.2.3-1: Probability that Estimated Ratio of On-treatment to Pre-treatment (Baseline) Value is Within 20% of True Value**

Intra-subject Standard Deviation (Log-scale)	0.2	0.3	0.4	0.5	0.6	0.7	0.8
N = 12	99%	90%	78%	68%	59%	52%	46%

For example, for a biomarker with an intra-subject standard deviation of 0.5 on the log-scale, if the true ratio of on-treatment to baseline value geometric means is 1.2 (20% increase from baseline), there is a 68% probability that the estimated ratio is within 0.96 to 1.44 (a percent change from -4% to 44% from baseline) with 12 evaluable participants. If the true ratio is 1.3 (30% increase from baseline), with the same variability, there is a 68% probability that the estimated ratio is within 1.04 to 1.56 (a percent change from 4% to 56% from baseline).

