#### 3 STUDY DESCRIPTION

## 3.1 Study Design

This is a Phase 1/2a, multicenter, open-label, non-randomized study of CD80/ $\alpha$ CD3 Oncolytic Virus (BMS-986277) alone and in combination with nivolumab for the treatment of metastatic or advanced epithelial tumors in male and female participants. There will be up to 4 sequential IV dose panels of BMS-986277 in monotherapy and 2 sequential IV dose panels of BMS-986277 in combination with nivolumab (480 mg Q4W).

The study will be conducted in 3 Parts:

- Part 1: a single agent monotherapy dose escalation of BMS-986277
  - Four dose levels:  $3 \times 10^{10}$  vp,  $3 \times 10^{11}$  vp,  $1 \times 10^{12}$  vp, and  $3 \times 10^{12}$  vp.
  - 6 week dose limiting toxicity (DLT) period to assess safety with multiple injections.
  - Dosing for the initial participants into each cohort in Part 1 will be staggered by 7 days to monitor for sentinel events
  - Participants will receive 3 cycles (28 day cycles; up to 6 max) of BMS-986277.
  - This part will determine the recommended dose to administer in the combination dose escalation (Part 2), based on the Bayesian Logistic Regression Model Recommended Dose (BLRM-RD) and overall clinical assessment of all available safety, pharmacokinetics (PK), pharmacodynamics, and efficacy data.
- Part 2: a combination dose escalation of BMS-986277 in combination with nivolumab in participants with low or mid CD8 tumor infiltrating lymphocytes (TILs) only
  - Participants will receive BMS-986277 at the BLRM-RD, or a lower dose than the BLRM-RD from Part 1.
  - Dosing for the initial participants into each cohort will be staggered by 7 days to monitor for sentinel events
  - BMS-986277 will be administered for up to three 28-day cycles, and nivolumab will be administered at 480mg Q4W for up to 26 cycles.
  - Low CD8 TILs are defined as CD8 < 2%

  - Mid CD8 TILs are defined as  $2\% \le CD8 \le 20\%$

- This part will determine the recommended Phase 2 dose (RP2D) based on the recommendations from the BLRM-copula and overall clinical assessment of all available safety, PK/pharmacodynamic, and efficacy data.
- Part 3: a 2 cohort dose expansion phase of BMS-986277 in combination with nivolumab in participants with low or mid CD8 tumor infiltrating lymphocytes (TILs) only
  - Participants will receive BMS-986277 at the RP2D established in Part 2 for up to 3 cycles, and nivolumab will be administered at 480mg Q4W for up to 26 cycles.

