  - Cohort 1 will treat participants with low CD8 TILs
  - Cohort 2 will treat participants with mid CD8 TILs

[figure not shown]
Participants with high CD8 TILs (defined as  $\geq$  20%) are not eligible for enrollment in Parts 2 and 3 of the study.

The study design schematic is presented in Figure 1.

The treatment regimens are described in more detail in Section 7.2

Details of the BLRM can be found in the Protocol Appendix  $10^2$ .

Figure 1: Study Design Schematic

For Parts 1 and 2, dosing of initial participants will be staggered by 7 days to mitigate against unexpected adverse drug reaction as follows:

- Lowest dose level: the first 3 participants may not begin dosing within 7 days of each other
- Other dose levels: the first 2 participants may not begin dosing within 7 days of one another

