#### **At Entrance:**

In the event that either of the following occur, the study team will consider whether the time relative to first dose is acceptable to be considered as the baseline assessment.

- Participants with a tumor tissue sample earlier than 35 days prior to first dose
- Participants whose baseline efficacy assessments are more than 28 days prior to first dose In the event that any of the following occur, the participants may be excluded from specific (or all) analyses upon study team agreement. Any exclusions due to relevant protocol deviations will be documented in the CSR.
- Participants in Parts 2 and 3 without an evaluable CD8 value prior to first dose.
- Participants without measurable disease at baseline (Inclusion Criteria 2.b).
- Participants in Parts 2 and 3 with a CD8 value  $\geq 20\%$  (Inclusion Criteria 2.f).
- Participants with screening ECOG performance status > 2 (Inclusion Criteria 2.g).
- Participants with prior exposure to checkpoint inhibitors or cytotoxic agents within 28 days prior to first dose (Inclusion Criteria 2.i and Exclusion Criteria 2.a).
- Participants with prior antiviral agents within 7 days prior to first dose or PEG-IFN within 14 days prior to first dose (Exclusion Criteria 2.e).

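### The SAP predates Part 3 Cohort 3 and still flags every participant with CD8 of 20% or more in Parts 2 and 3 as a deviation open to exclusion, although the current protocol admits them

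*SAP*

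**What the plan says.** **SAP.** The revision history in Section 1 says that v1.0 covers changes up to Revised Protocol 03. Section 3.1 describes "Part 3: a 2 cohort dose expansion phase of BMS-986277 in combination with nivolumab" and says that participants with high CD8 "are not eligible for enrollment in Parts 2 and 3 of the study". Section 8.2.3, under At Entrance, lists "Participants in Parts 2 and 3 with a CD8 value" of 20% or more, citing Inclusion Criterion 2.f, among the deviations for which "the participants may be excluded from specific (or all) analyses upon study team agreement". Any such exclusion is to be documented in the CSR.

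**Protocol (Revised 06).** Inclusion 2.e states "All comers CD8 TIL are permitted in Parts 1 and 2", provided that at least 3 low or mid participants are evaluated at each Part 2 dose level. Inclusion 2.f classifies CD8 of 20% or more as high, one of three Part 3 categories that determine cohort. Section 10.1.2.3 states "Cohort 3 is a monotherapy expansion of BMS-986277 which will treat participants with high CD8 TILs". The document history records an added expansion cohort in Revised Protocol 05.

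**Response window.** Protocol 9.1.3 reads "BOR is defined as the best response designation over the study as a whole, recorded between the dates of first dose until the last tumor". The window thus ends at the final scan ahead of any later anticancer treatment, or at first progression for those treated beyond it. SAP 5.2.1 closes the window at first objectively documented progression or subsequent anticancer therapy. Protocol 7.1.6 says of Cohort 3: "Following 2 cycles of BMS-986277 monotherapy, participants may receive optional nivolumab treatment (480 mg Q4W) for up to 26 cycles". This is subject to continued eligibility. Protocol Section 7 lists nivolumab as study treatment.

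**The concern.** A programmed deviation rule cites Inclusion 2.f to flag people whom the current 2.f admits. The SAP states that it supersedes the protocol's statistical considerations, so this cannot be dismissed as background text. Exclusion is not limited to efficacy: it can reach any analysis, and the SAP gives neither criteria nor a deadline for the team's decision.

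At stake are the whole of Cohort 3 and the CD8-high participants in Part 2. The latter also matter to Protocol 10.3.7, which models response against the diagnostic assay in Part 2 and Part 3 Cohorts 1-2. If that assay is CD8, Part 2 is the only source of values of 20% or more, and excluding them would cut off the upper end of the range.

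The secondary point is one of interpretation. If nothing splits Cohort 3 at the first nivolumab dose, its ORR and PFS describe a sequence of two treatments, and a reader cannot tell which part of the result belongs to the monotherapy phase.

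**Working it through.** **1. The passages side by side**

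| Item | SAP v1.0 | Current protocol |
|---|---|---|
| CD8 ≥ 20%, Part 2 | Ineligible (3.1); deviation (8.2.3) | Permitted (2.e) |
| CD8 ≥ 20%, Part 3 | Ineligible (3.1); deviation (8.2.3) | Defines Cohort 3 (2.f, 10.1.2.3) |
| Part 3 cohorts | 2, combination only (3.1) | 3, the third being monotherapy with optional nivolumab (5.1.3) |
| Nivolumab day, Part 3 | Day 15 (Table 7) | Day 15 in Cohorts 1-2; Day 1 from Cycle 3 in Cohort 3 (7.1.5, 7.1.6) |
| AE window, Part 3 | 100 days for all (7.1.2, 8.6) | 60 days if BMS-986277 only, 100 if nivolumab was given (Table 2-5, 9.2.1) |

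**2. Who is flagged**

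- Cohort 3: 12 evaluable plus about 20% (Protocol 10.1.2.3) is 12 × 1.20 = 14.4, or 15. All are flagged by definition.
- Part 2: up to 12 per dose level (5.1.2), of whom at least 3 must be low or mid. The largest number flagged at a level is 12 − 3 = 9.

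**3. Cohort 3 precision**

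Protocol Table 10.1.2.3-1 reproduces with error on the log scale ~ Normal(0, SE), SE = SD × √(2/n), and probability Φ(ln 1.2 / SE) − Φ(ln 0.8 / SE). For SD 0.5 and n = 12, SE = 0.204 and the probability is Φ(0.893) − Φ(−1.093) = 67.7%, against 68% stated. Across SD 0.2 to 0.8 the results are 98.4, 89.7, 78.2, 67.7, 59.1, 52.1 and 46.4%, against 99, 90, 78, 68, 59, 52 and 46%.

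If the exclusion rule were applied in part, precision at SD 0.5 would fall as follows:

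| n kept | 12 | 10 | 8 | 6 | 3 |
|---|---|---|---|---|---|
| Probability | 68% | 63% | 58% | 52% | 38% |

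Applied in full, it leaves n = 0.

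**4. Timeline for the secondary point (first dose = Day 1)**

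- Cycle 3 Day 1 = 1 + 28 + 28 = Day 57; with ±3 days (Table 2-5), Days 54 to 60.
- First scan = 1 + 56 = Day 57; with ±7 days, Days 50 to 64.
- Earliest confirmation of a first-scan response, at least 4 weeks later = 50 + 28 = Day 78. The next scheduled scan is 1 + 112 = Day 113.

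Day 78 is later than Day 60. A participant who starts nivolumab on schedule therefore cannot have a response that is both seen and confirmed on scheduled scans before nivolumab. The first scan itself may fall on either side of the first nivolumab dose.

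**5. Possible size of the mixing (assumption)**

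The documents give no nivolumab response rate for CD8 of 20% or more. Take a true monotherapy ORR of 0 and a nivolumab-phase rate q of 6%, 20% or 40%. If m of 12 participants start nivolumab without documented progression, the expected cohort ORR is m × q / 12.

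| m | q = 6% | q = 20% | q = 40% |
|---|---|---|---|
| 6 | 3% | 10% | 20% |
| 12 | 6% | 20% | 40% |

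**The case against.** **Version lag.** The strongest reply on the deviation rule is that SAP v1.0 is simply behind the protocol. SAP Section 1 waives an amendment only for protocol changes that do not affect the statistical methodology, and Protocol 10.3 has the SAP finalized before the final lock, so an update is already implied. A relevant deviation is defined as a departure from the protocol, which a Cohort 3 participant has not made. Exclusion is optional, needs team agreement and is documented, and the final efficacy analysis stays on all treated participants. All of this limits the likely harm. It does not cure the rule: SAP 8.2.2 ties a separate eligibility listing to the criteria at enrolment, and the amendment sentence in 8.2.3 covers deviations missing from the list, not wrong entries on it.

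**Stronger readings of the response window.** A reader might infer that nivolumab responses are being credited to BMS-986277 alone. No passage labels the Cohort 3 ORR that way. Summaries are by cohort, the SAP efficacy objective names only the combination, and the SAP leaves grouping schemes to a data presentation plan not available here. Responses after documented progression are not counted. Week 8 responders need Medical Monitor agreement before nivolumab, so some may stay unmixed. A response first seen before nivolumab and confirmed during it arose on monotherapy. A reader might also infer that the monotherapy activity question is lost. It is not: Part 1 supplies nivolumab-free data from up to 24 participants initially, and Cohort 3 was set up and sized for pharmacodynamics.

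What stands is the absence of any stated cut. Because nivolumab is study treatment, the natural reading is that it does not close the window. The heading of Protocol 7.1.6 nevertheless calls it subsequent treatment, so programmers could differ.

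**Conclusion.** The deviation rule is wrong against the current protocol and must be corrected. It flags 100% of Cohort 3 (about 12 to 15 participants) and up to 9 of 12 at any Part 2 dose level. These are maxima of those exposed to discretionary exclusion, not a forecast of those who would be removed. The documents do not say that exclusions would follow sight of results; they set no deadline in an open-label study.

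The response-window point is real but secondary. It concerns participants who start nivolumab without documented progression. Its size depends on how many do so and on their nivolumab response rate, neither of which the documents give; the 3% to 40% range above rests on the stated assumptions.

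It would go too far to conclude that Cohort 3 cannot be validly analysed. The SAP can be amended before lock, and the pharmacodynamic estimate that sizes the cohort reproduces and makes no use of best overall response.

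**What to change.** Amend the SAP before database lock:

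1. In 3.1, replace the two-cohort description and the ineligibility statement with the current Part 2 and Part 3 populations.
2. In 8.2.3, delete the CD8 ≥ 20% trigger for Part 2 and Cohort 3. Flag instead a CD8 value inconsistent with the assigned Part 3 cohort. The existing entry for a missing CD8 value can stay.
3. Add Cohort 3 to the treatment-regimen, sample-size and exposure sections, and reconcile the AE windows with the protocol's collection periods, separating participants who do and do not receive nivolumab.
4. State whether first nivolumab in Cohort 3 closes the best overall response, duration of response and PFS windows. Add a descriptive summary of response and PFS with assessments cut at first nivolumab dose, beside the whole-sequence result. Note with it that scheduled scans allow no confirmed pre-nivolumab response in those who start on time.

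Two further steps might be considered but are not needed: taking a new tumour baseline at the last pre-nivolumab scan, and making an unconfirmed Week 8 response the monotherapy result. The first departs from Appendix 7, which judges partial response against the baseline sum; the second departs from the confirmation rule in Protocol 9.1.

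The cost is a SAP amendment and a few extra tables. Trial conduct and data collection do not change.

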#### **On-Treatment:**

- Participants receiving treatment that is different than what they were assigned
  - In the event that this occurs, the participant may be grouped with others receiving the actual treatment for analyses, if such a group exists.
- Participants receiving anti-cancer therapy (chemotherapy, hormonal therapy, immunotherapy, or non-palliative radiation therapy; standard or investigational) before the last dose of study drug
  - In the event that this occurs, this will be treated as the participants' subsequent therapy for certain efficacy assessments described in Section 5.2.1.

## 8.3 Study Population

#### 8.3.1 Disposition of Participants

Status of participants at the end of pre-treatment period will be summarized and listed for the All Enrolled population. Status of participants at the end of treatment period will be summarized by part, dose level/cohort, indication, and overall, based on the All Treated population. In addition, the status of participants at the end of each study period will be summarized as appropriate. A listing will be provided for those participants who were treated and reason for discontinuation of treatment or not being followed will be described.

# 8.3.2 Demographics and Other Baseline Characteristics

#### **Summary:**

Descriptive statistics will be summarized for the following baseline characteristics for the All Treated population by part, dose level, cohort, indication, biomarker level, and overall.

- Age at Consent (in years); age category (<65, ≥65), female age category (≤50, >50, NA for male - for the TNBC indication only)
- Sex at Birth
- Race
- Ethnicity (for US only)
- Region (North America, EU, Asia, Rest of World)
- Height at Baseline
- Weight at Baseline
- ECOG Performance Status at Baseline
- Disease characteristics at Baseline
  - CRC: Stage at study entry, microsatellite instability status, mismatch repair status, KRAS status, and BRAF status
  - Ovarian: Stage at study entry, BRCA1 status and BRCA2 status
  - PC: Stage at study entry and disease classification subtype
  - PRC: Stage at study entry
  - TNBC: Stage at study entry, disease classification subtype, BRCA1 status, BRCA2 status, ER status, PR status, and HER-2 status
  - UC: Stage at study entry

